6.4.2.6 Visit 6 (Day 113 ± 3 days)

- Patient-reported outcomes, before other interactions with study staff
 - o Lupus Activity Patient Global Assessment
 - PROMIS-29 Short Form
 - PROMIS Item Bank v2.0 Cognitive Function
 - Fibromyalgia Symptom Scale
- Confirm date of last menstrual period in women of childbearing potential
- Record concomitant medications
- Vital signs: weight, blood pressure, pulse, respiratory rate, and temperature
- Physical examination
- Physician assessments (all scores will be calculated centrally)
 - o 66/68 joint count
 - SELENA SLEDAI and Flare Index
 - o BILAG 2004
 - Physician's Global Assessment
- AE monitoring
- Blood tests
 - Hematology: CBC with differential cell count and platelets

- Chemistry: Complete metabolic panel, including electrolytes, renal function, and liver function tests
- o CRP
- Anti-dsDNA antibody titers, C3, and C4 levels
- Blood draws for mechanistic studies
 - Whole blood: TruCulture tubes; pro-inflammatory cytokines
 - \circ RNA: Type 1 IFN α gene signature
 - Serum: future use (if subject provided written consent)
 - PBMC: future use (if subject provided written consent)
- Urine tests
 - Urinalysis: microscopic evaluation, and spot protein/creatinine
 - o Urine βHCG pregnancy test in women of childbearing potential

6.4.2.7 Early Withdrawal Visit

If a subject is withdrawn from the study or discontinues the study on or before Visit 1 (Day 1), no additional procedures should be done. If withdrawal or discontinuation is after Visit 1 (Day 1) and at the time of a scheduled visit, the procedures scheduled for that visit should be done and an Early Withdrawal Visit should be done 28 ± 3 days after the last dose of study product, unless consent is withdrawn. If withdrawal or discontinuation is after Visit 1 (Day 1) and not at the time of a scheduled visit, then an unscheduled visit should be done as soon as possible and include evaluations and laboratory safety testing as appropriate for the reasons for withdrawal or discontinuation, and an Early Withdrawal Visit should be done 28 ± 3 days after the last dose of study after the last dose of study product, unless consent is withdrawal withdrawal Visit should be done 28 ± 3 days after the reasons for withdrawal or discontinuation, and an Early Withdrawal Visit should be done 28 ± 3 days after the last dose of study product, unless consent is withdrawal.

- Patient-reported outcomes, before other interactions with study staff
 - ARCI-M questionnaire
 - o Lupus Activity Patient Global Assessment
 - PROMIS-29 Short Form
 - PROMIS Item Bank v2.0 Cognitive Function
 - Fibromyalgia Symptom Scale
 - Treatment Satisfaction Survey, if withdrawal is prior to Visit 5 (Day 85)
- Confirm date of last menstrual period in women of childbearing potential
- Record concomitant medications
- Vital signs: weight, blood pressure, pulse, respiratory rate, and temperature

- Physical examination
- Physician assessments (all scores will be calculated centrally)
 - o 66/68 joint count
 - SELENA SLEDAI and Flare Index
 - o BILAG 2004
 - o Physician's Global Assessment
 - Treatment Satisfaction Survey, if withdrawal is prior to Visit 5 (Day 85)
- AE monitoring
- Blood tests
 - Hematology: CBC with differential cell count and platelets
 - Chemistry: Complete metabolic panel, including electrolytes, renal function, and liver function tests
 - o CRP
 - Anti-dsDNA antibody titers, C3, and C4 levels
- Blood draws for mechanistic studies
 - Whole blood: TruCulture tubes; pro-inflammatory cytokines
 - \circ RNA: Type 1 IFN α gene signature
 - Serum: future use (if subject provided written consent)
 - PBMC: future use (if subject provided written consent)
- Urine tests
 - Urinalysis: microscopic evaluation, and spot protein/creatinine
 - \circ Urine β HCG pregnancy test in women of childbearing potential
- Collect any remaining study product and count and record number of returned capsules

6.4.3 **Visit Windows**

All study procedures should be performed within the designated visit window (i.e., ± 3 days) for each scheduled visit (see Table 3, *Schedule of Events* (below)). Whenever possible, a rescheduled visit should remain within the designated visit window. The coordinating center should be notified if the study procedures for any scheduled visit cannot be performed within the designated window.

6.4.4 **Unscheduled Visits**

Subjects will be instructed to call study personnel to report any abnormalities during the intervals between study visits and to come to the study site if medical evaluation is needed and the urgency of the situation permits. An unscheduled visit will be made, if necessary, for medical issues that arise between study visits. For emergency and other unscheduled visits to a medical facility other than the study site, medical records will be obtained by the site investigator or qualified designee.

If an unscheduled visit is necessary to assess the subject for safety purposes, the following evaluations should be obtained, at a minimum:

- Record concomitant medications
- Vital signs: weight, blood pressure, pulse, respiratory rate, and temperature
- Physical examination as relevant to the reason for the unscheduled visit
- AE monitoring
- Urine βHCG pregnancy test in women of childbearing potential
- Laboratory tests as relevant to the reason for the unscheduled visit

Table 5. Schedule of Events (Screening through	0	Treatment					Post Treatment		
Time Point	Screening ^A	Visit 1	Visit 2	Visit 3	Visit 4	Visit 5	Visit 6	Early Withdrawal	Unscheduled Visit
Visit Windows (Days)	Up to -42	Day 1	Day 15 ± 3	Day 29 ± 3	Day 57 ± 3	Day 85 ± 3	Day 113 ± 3	Visit (if needed)	
Clinical Blood Draw (mL)	20-23	11	8	11	11	11	11	11	11
Research Blood Draw (mL)	NA	48.5	34	10.5	NA	40.5	40.5	40.5	NA
Visit Draw Total (mL)	20-23	59.5	42	21.5	11	51.5	51.5	51.5	11
General Assessments				•	•	1	I	I	•
Informed Consent	Х								
Demographics	Х								
Verify Eligibility Criteria		Х							
Medical History	Х								
Assess reproductive and birth control status	Х								
Last menstrual period	Х	X ^B		X ^B	X ^B	X ^B	X ^B	X ^B	
Prior/ Concomitant medications	Х	Х	Х	Х	Х	Х	Х	Х	Х
Physical examination	Х	Х		Х	Х	Х	Х	Х	Х
Register subject in IVRS system	Х								
Randomization, prior to Day 1	X								
Vital signs: Weight, blood pressure and pulse ^C , respiratory rate, and temperature (& height at Visit 1)	X	х	X	X	X	х	X	X	Х
Adverse event monitoring		Х	Х	Х	Х	Х	Х	Х	Х
12-lead electrocardiograms, QT/QTc analyses	Х	XD				Х			
Patient Reports	 			-	-	•			J
Maximum daily pain NRS score ^E				Report	ed daily by sub	ject via IVRS			
Review reported pain NRS scores			Site	e personnel will	l review subject	reported data	each week		
Addiction Research Center Inventory-Marijuana (ARCI-M)		XD		X		X		X ^F	
Lupus Activity Patient Global Assessment		Х		Х	Х	Х	Х	Х	
PROMIS-29 Short Form		Х		Х	Х	Х	Х	Х	
PROMIS Item Bank v2.0 - Cognitive Function		Х		Х	Х	Х	Х	Х	
Fibromyalgia Symptom Scale	х	Х				Х	Х	Х	
Treatment Satisfaction Survey ^G						Х		X ^G	
Physician Assessment							I		1
66/68 Joint Count		Х		X	X	Х	Х	Х	
SELENA SLEDAI	X	X	1	X	X	X	X	X	1
BILAG 2004	X	X		X	X	X	X	X	1
Physician's Global Assessment	X	X		X	X	X	X	X	
Treatment Satisfaction Survey		21				X	21	X ^G	

Table 3: Schedule of Events (Screening through Post Treatment)

				Treatment			Post T		
Time Point	Screening ^A	1	2	3	4	5	6	Early	Unscheduled
Visit Windows (Days)	Up to -42	Day 1	Day 15 ± 3	Day 29 ± 3	Day 57 ± 3	Day 85 ± 3	Day 113 ± 3	Withdrawal Visit (if needed)	Visit
Clinical Laboratory Assessments									
Infectious Disease: Hepatitis B and C tests, human immunodeficiency virus ^H	Х								
Tuberculosis screening test ¹	Х								
Follicle stimulating hormone ^J	Х								
Hematology: CBC with differential cell count and platelets	Х	\mathbf{X}^{L}	Х	Х	Х	Х	Х	Х	X ^M
Chemistry: Complete metabolic panel ^K	Х	XL	Х	Х	Х	X	Х	Х	X ^M
Anti-dsDNA antibodies, C3, C4	Х	X^L		Х	Х	X	Х	Х	X ^M
C-reactive protein		X^L		Х		Х	Х	Х	X ^M
Urinalysis: Microscopic, & spot protein/creatinine	Х	X^L		Х	Х	Х	Х	Х	X ^M
Urine pregnancy test ^B	X ^N	X^L		Х	Х	Х	Х	Х	X ^M
Blood Draws for Mechanistic Specimen Collection					•	•			•
Whole blood Pro-Inflammatory Cytokine Studies (3mL)		\mathbf{X}^{L}		Х		Х	Х	Х	
Plasma: Metabolipidomic profile/JBT-101 plasma concentrations and metabolites (4mL)		X^{DL}	Х						
RNA: IFNα signature (2.5mL)		X^L		Х		X	Х	Х	
Serum: Future Use ^O (5mL)		X^L		Х		Х	Х	Х	
PBMC: Future Use ^o (30mL)		X^L	Х			Х	Х	Х	
Study Product			· ·	•			•	•	•
Dispense study product ^P		Х		Х	Х				
Administer study product in clinic ^Q		Х							
Study product pill count			Х	Х	Х	Х	X (if needed)	X (if needed)	

A. The screening period can be any duration between 7 and 42 days prior to Visit 1 (Day 1), provided the duration is adequate to ensure the subject meets all inclusion and exclusion criteria and drug can be shipped to the site on time for that subject. Screening can take place over more than one visit to the clinic. Screening laboratory tests, other than HIV, hepatitis, or pregnancy testing, can be repeated at the investigator's discretion.

- B. For women of childbearing potential.
- C. Seated (> 5 minutes) blood pressure and pulse.
- D. Will be measured at Visit 1 (Day 1) both before and 2.5 to 3.5 hours after administration of study product in the clinic.
- E. Record within 24 hours after most recent diary entry to prevent reporting of the same data.
- F. ARCI-M will be assessed at the Early Withdrawal Visit if a subject is withdrawn from the study or discontinues the study prior to Visit 6 (Day 113).
- G. At the end of treatment, both the subject and physician will complete a Treatment Satisfaction Survey. If a subject withdrawals from treatment prior to Day 85, the Treatment Satisfaction Survey will be completed at the Early Withdrawal Visit.
- H. Infectious disease screen including HIV antibody, hepatitis B surface antigen, hepatitis C virus (HCV) antibody with HCV RNA (PCR) if antibody positive (unless documented as negative within 12 weeks prior to the Screening visit).

- I. TB testing will be done centrally using a QuantiFERON® blood test. Testing is optional if skin or blood testing was done within 12 months before Visit 1 (Day 1), with documented negative results. See section 6.1.10 *Tuberculosis Screening* for repeat testing options.
- J. For women > 45 and ≤ 55 years of age with no menses for < 2 years.
- K. Complete metabolic panel includes at least glucose, urea nitrogen, creatinine, sodium, potassium, chloride, carbon dioxide, calcium, total protein, albumin, total bilirubin, alkaline phosphatase, aspartate aminotransferase, alanine aminotransferase, and calculated glomerular filtration rate.
- L. Blood and urine tests will be performed prior to study product administration.
- M. Laboratory tests as relevant to the reason for the unscheduled visit.
- N. Pregnancy test at screening can be done through a blood or urine test.
- O. If the subject provides written informed consent, blood samples, including serum, plasma, mRNA, and PBMC culture supernatants, will be stored for future unspecified studies related to JBT-101 or SLE.
- P. Study product will be dispensed in women of childbearing potential only if urine pregnancy test is negative.
- Q. The first dose of study product at Visit 1 (Day 1) will be taken in clinic from the dispensed study product. The subject will be observed for 30 minutes or until stable in the judgment of the investigator, whichever is longer.

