Expected AEs in a general population include events such as mild changes in vital signs, sore throats, mild skin, upper or lower respiratory tract, or genitourinary infections requiring topical or oral antibiotics, asymptomatic bacteriuria, headaches, nausea, mild rashes, and minor accidents. Mild abnormalities in laboratory testing of CBC testing, platelets, differential cell counts, metabolic panels including liver function tests and electrolytes, and urinalyses are expected to occur in a general population.

Abrupt discontinuation of treatment with JBT-101 has not been shown to cause any harmful effects in previous studies; therefore, study product may be stopped without tapering or adding additional treatments. If a subject has received clinical benefit from JBT-101, then his/her disease activity may or may not worsen after discontinuation of JBT-101. To reduce this risk of disease flare, subjects will continue their standard-of-care medication throughout the study and during the follow-up period. Subjects will have follow-up safety evaluation and testing of disease activity 28 ± 3 days after the end of the planned active treatment period or after withdrawal or discontinuation of study product.

Subjects will be instructed to call the site investigator or treating physician if they experience an AE (whether or not they determine it to be related to the study) and may be evaluated for potential toxicity at an unscheduled visit.

Please see the IB for JBT-101 for further information about risk.

1.5.2 **Potential Benefits**

No physical, psychological, social, legal, or any other benefits are claimed for individual SLE subjects who chose to participate in this study. Based on biologic effects of JBT-101 and other preferential CB2 agonists in *in vitro* and *in vivo* models of inflammation and various diseases, it is reasonable to test JBT-101 for evidence of efficacy in SLE in this study. The information that will come from this study will address effects of JBT-101 on efficacy, safety, tolerability, and biomarkers of inflammation in SLE subjects. This information will be used in decision making about whether to progress JBT-101 to future pivotal clinical studies, as a step toward approval by regulatory agencies for treatment of SLE.

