5.3 Administration of Study Product

JBT-101 will be self-administered orally b.i.d., with at least 8 hours between doses and without regard to fed state. See Section 3.1, *Description of Study Design*; Table 1 for morning and evening dosing for the 4 cohorts. The first dose of JBT-101 at Visit 1 (Day 1) will be taken in the clinic, and the subjects will be observed in the clinic for at least 30 minutes after this dose or longer, until, in the opinion of the investigator, vital signs and clinical symptoms are acceptable for the subject to leave the clinic. After this observation period, subjects must still be available for additional assessments 2.5 to 3.5 hours after administration of the study product.

JBT-101 should be taken in the following way:

- JBT-101 and placebo capsules should be swallowed whole, with liquid as helpful, and should not be broken, chewed or opened. Morning and evening doses should be at least 8 hours apart.
- If a dose of JBT-101 or placebo is missed, it should be taken as soon as possible on the same day, as long as the other dose that day can be timed to be at least 8 hours separate from the time of the missed dose. If it is missed for the entire day, it should not be made up.
- Doses can be taken without regard to fed state.

Subjects who take more than the prescribed dose of JBT-101 or placebo should be instructed to seek emergency medical care, if needed, and to contact the study staff as soon as possible.

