5.4.2 Management of Potential Risks to Study Product

Severe symptoms related to the potential risks of JBT-101 may necessitate stopping study drug. Stopping study drug is not a reason for withdrawal from the study, but a subject may be withdrawn at the discretion of the PI if deemed it is in the subject's best interest.

For subjects who experience potential CB1/CB2 mediated AEs (fatigue, dizziness, decreased concentration, feeling "weird", lightheadedness, asthenia, somnolence, GI disturbances such as nausea or vomiting, or dry mouth), treatment for symptoms should be prescribed as needed, and study treatment may be withheld at discretion of PI.

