5.8.1.1 Procedures for Discontinuation of Protocol-Specified Treatment Requirements

Whenever possible, subjects who have been discontinued from study treatment should complete all scheduled study visits including all exams, procedures, assessments, and tests for the duration of the study. Furthermore, if discontinuation is due to safety concerns, subjects will be given appropriate care under medical supervision beyond the last scheduled study visit, if necessary, until the symptoms of any AE resolve or the subject's condition becomes stable. If the site Principal Investigator (PI) determines that completion of these visits is not clinically appropriate for the subject or if the subject or subject's guardian elects not to complete these visits, the subject will be withdrawn from the study per the guidelines in Section 5.8.2.1, *Procedures for Subject Withdrawal from the Study*.

5.8.2 **Subject Withdrawal from the Study**

When a subject is withdrawn from the study, protocol-specified treatment requirements are discontinued, and study-related visits, exams, procedures, assessments, tests and data collection are terminated. Individual subjects will be withdrawn from the study under the following conditions:

- The subject or subject's guardian withdraws consent
- If the subject elects to participate in any other sort of study or clinical trial (excluding observational registries or cohorts), the subject may be withdrawn at the discretion of the DAIT/NIAID
- Subject non-compliance with treatment regimens or failure to keep appointments

5.8.2.1 **Procedures for Subject Withdrawal from the Study**

All withdrawn subjects will have a follow-up visit after study product is discontinued for final safety monitoring. The timing of the Early Withdrawal Visit in this study is 28 ± 3 days after study product is discontinued. Assessments will be the same for subjects who withdraw before completing all dosing and those who complete all dosing. Subjects who withdraw consent will be asked to complete the Early Withdrawal Visit; however, they will not be required to complete the visit.

Subjects who are withdrawn due to pregnancy will be followed according to the procedures outlined in Section 6.1.9, *Pregnancies*.

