6.4.2.1 Visit 1 (Day 1)

- Verify eligibility criteria
- Patient-reported outcomes, before other interactions with study staff
 - ARCI-M questionnaire (Pre-Dose)
 - Lupus Activity Patient Global Assessment
 - PROMIS-29 Short Form
 - PROMIS Item Bank v2.0 Cognitive Function
 - Fibromyalgia Symptom Scale
- Confirm date of last menstrual period in women of childbearing potential

- Record prior medications
- Vital signs: Height, weight, blood pressure, pulse, respiratory rate, and temperature
- Physical examination
- Physician assessments (all scores will be calculated centrally)
 - o 66/68 joint count
 - SELENA SLEDAI and Flare Index
 - o BILAG 2004
 - Physician's Global Assessment
- AE monitoring
- **Before** study product administration
 - Blood tests
 - Hematology: CBC with differential cell count and platelets
 - Chemistry: Complete metabolic panel, including electrolytes, renal function, and liver function tests
 - CRP
 - Anti-dsDNA antibody titers, C3, and C4 levels
 - o Blood draws for mechanistic studies
 - Whole blood: TruCulture tubes; pro-inflammatory cytokines
 - Plasma: metabolipidomic profile, and JBT-101 plasma concentrations and metabolites; sampled ≥ 2 hours after last solid meal, if possible.
 - RNA: Type 1 IFNα gene signature
 - Serum: future use (if subject provided written consent)
 - PBMC: future use (if subject provided written consent)
- Urine tests before study product administration
 - Urinalysis: microscopic evaluation, and spot protein/creatinine
 - Urine βHCG pregnancy test in women of childbearing potential
- Triplet 12 lead ECGs for medically significant abnormalities and QT/QTc interval prior to study product administration
- Dispense study product according to randomization schedule. Women of child bearing potential must have negative urine βHCG pregnancy test prior to dispensing study product
- Administer study product in clinic and record time of dose

- Observe subject for at least 30 minutes in clinic, until stable in the judgment of the investigator
- 2.5 to 3.5 hours after study product administration
 - ARCI-M questionnaire (Post-Dose)
 - Triplet 12 lead ECGs for QT/QTc interval
 - Blood draws for mechanistic studies
 - Plasma: metabolipidomic profile, and JBT-101 plasma concentrations and metabolites; sampled ≥ 2 hours after last solid meal, if possible
- Reminders:
 - Remind subjects to bring the bottles of study drug with them to their next visit.

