7.3 Collection and Recording of Adverse Events

7.3.1 **Collection Period**

AEs of Grade 2 and above will be collected from time of signing of informed consent until the subject completes study participation, or until 30 days after he/she prematurely withdraws (without withdrawing consent), or is withdrawn from the study. See Section 7.4, *Grading and Attribution of Adverse Events* for grading criteria.

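### The Early Withdrawal Visit exemption in section 6.4.2.7 is tied to Visit 1 instead of the first dose, so a subject dosed and withdrawn on Day 1 loses the safety visit that 5.8.2.1 and 1.5.1 require

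*Protocol*

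**What the plan says.** Section 6.4.2.7 has three branches.

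- **Departure no later than Visit 1.** If the subject is withdrawn or "discontinues the study on or before Visit 1 (Day 1), no additional procedures should be done".
- **Departure after Visit 1, at a scheduled visit.** That visit's procedures are done, and the Early Withdrawal Visit follows 28 ± 3 days after the last dose unless consent is withdrawn.
- **Departure after Visit 1, between visits.** An unscheduled visit is held as soon as possible, and the Early Withdrawal Visit follows on the same timing and condition.

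Dosing falls inside Visit 1. Section 5.3 states: "The first dose of JBT-101 at Visit 1 (Day 1) will be taken in the clinic". The Visit 1 procedure list in 6.4.2.1 includes "Administer study product in clinic and record time of dose".

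Two other sections set the follow-up rule by study product. Section 5.8.2.1 states: "All withdrawn subjects will have a follow-up visit after study product is discontinued for final safety monitoring", timed at 28 ± 3 days; subjects who withdraw consent are asked to attend but not obliged to. Section 1.5.1 promises safety evaluation "28 ± 3 days after the end of the planned active treatment period or after withdrawal or discontinuation of study product".

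**The concern.** The exemption makes sense for someone who leaves before taking study product. It is keyed to the visit, however, and the first dose is taken during that visit, so it also covers a subject who has been exposed.

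Such a subject belongs to the safety population, which section 8.2.3 defines by initiation of treatment. Section 7.3.1 collects their adverse events "until 30 days after he/she prematurely withdraws" provided consent stands. The visit at which they would be examined and have blood and urine taken is the one that 6.4.2.7 removes.

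Nothing here touches the primary endpoint, the power or the type I error rate. What is at stake is safety follow-up after exposure in the first trial of this drug in SLE.

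**Working it through.** No sample-size or power figure is involved, so the check sets the sections side by side for one case: a subject dosed at Visit 1 who leaves the study later that day with consent intact.

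| Section | Condition | Applies to this subject? | Result |
|---|---|---|---|
| 6.4.2.7, first branch | leaves no later than Visit 1 | yes | nothing further is done |
| 6.4.2.7, second branch | leaves after Visit 1, at a scheduled visit | no | – |
| 6.4.2.7, third branch | leaves after Visit 1, between visits | no | – |
| 5.8.2.1 | any withdrawn subject | yes | visit 28 ± 3 days after product stops |
| 1.5.1 | withdrawal or discontinuation of product | yes | safety evaluation at 28 ± 3 days |

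The first row and the last two cannot all be followed. No section makes an exception for a dosed subject. Table 3 footnotes F and G schedule Early Withdrawal assessments for withdrawal before Visit 6 and before Day 85 respectively, with no Day 1 exclusion.

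**Can the case occur?** There are two routes that leave consent intact.

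1. Section 5.4.2 says that stopping drug is not in itself a reason for withdrawal, "but a subject may be withdrawn at the discretion of the PI" if that is in the subject's best interest.
2. Under 5.8.1.1, a subject taken off treatment is withdrawn if the investigator judges the remaining visits clinically inappropriate, or if the subject elects not to complete them. A Grade 3 or higher event at least possibly related to study product stops treatment (5.8.1), and it could follow the first dose.

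**What is lost.** Table 3 footnote L says of Visit 1: "Blood and urine tests will be performed prior to study product administration". The scheduled assessments after the Day 1 dose are the ARCI-M, the triplicate ECGs and the plasma draw at 2.5 to 3.5 hours (6.4.2.1). For a Day 1 leaver, the Early Withdrawal Visit is the only scheduled post-dose hematology, chemistry, urinalysis and pregnancy test.

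**Scale.** The protocol gives no rate of Day 1 exits. The nearest figures, in 1.3.4, are withdrawals following a treatment-emergent adverse event at any time on JBT-101:

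- systemic sclerosis trial: 1/27 = 3.7%
- cystic fibrosis trial: 4/61 = 6.6%
- pooled: (1 + 4)/(27 + 61) = 5/88 = 5.7%
- applied to the 3 × 25 = 75 active subjects planned here: 75 × 5/88 = 4.3

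This counts such withdrawals over whole trials in other diseases. Same-day exits with consent intact would be a small part of it, and no Day 1 exit is described. It is shown for scale and is not an estimate of the number affected.

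**The case against.** The case for leaving the text alone has four parts.

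- **The requirement is already in the protocol.** Section 5.8.1.1 sends a subject who is taken off treatment and then withdrawn to 5.8.2.1, and 5.8.2.1 makes the visit mandatory. This is true, but it confirms the conflict: one section sends a dosed Day 1 leaver to the visit, and the paragraph that governs that visit tells the site to do nothing.
- **The intent can be recovered.** Subjects are randomized at least 7 days before Visit 1. At Visit 1 eligibility is verified and women of childbearing potential need a negative pregnancy test before product is dispensed, so some subjects could leave at Visit 1 undosed. The sentence was probably written for them. That is a fair reading of intent, but the wording does not limit it to them.
- **The group is close to empty.** The withdrawal conditions listed in 5.8.2 are withdrawal of consent, joining another study, and non-compliance or missed appointments. The first makes the visit optional, and the others are unlikely within hours of a dose taken in the clinic. A first-dose reaction normally leads to stopping drug with follow-up continued. This stands, and it limits the weight of the point.
- **The clinical yield is low.** The single-dose half-life is 3.7 to 5.6 hours (1.3.4), so 28 days (672 hours) is at least 672/5.6 = 120 half-lives after one dose. The Day 1 post-dose assessments, 30-day adverse event collection and pregnancy reporting all remain. This also stands. It bears on how much the visit would find, not on whether the sections agree.

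**Conclusion.** The concern holds. Section 6.4.2.7 is wrong as written for a subject who is dosed at Visit 1 and leaves the study the same day with consent intact, and it contradicts 5.8.2.1 and 1.5.1 for that subject. The practical weight is low. The number affected is unknown and probably very small, and each such subject loses one visit, which holds all of their scheduled post-dose blood and urine safety tests.

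The conclusion rests on a literal reading of 6.4.2.7; a site that followed 5.8.2.1 instead would still hold the visit. No efficacy analysis is affected. The change is worth making because the text gives sites opposite instructions about follow-up after exposure.

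**What to change.** In 6.4.2.7, make receipt of study product the boundary:

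- in the first branch, replace the reference to leaving on or before Visit 1 with *before the first dose of study product*;
- in the second and third branches, replace both references to leaving after Visit 1 with *after the first dose of study product*.

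Every dosed subject then has the 28 ± 3 day Early Withdrawal Visit unless consent is withdrawn. A subject leaving during Visit 1 after dosing would also fall under the second branch, which tells the site to do that visit's procedures. The boundary would match the one used in 3.1.1.1 (subjects who never initiate treatment), 8.2.1 and 8.2.3.

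The cost is a wording change in one paragraph of a protocol amendment. It adds no visit beyond those 5.8.2.1 already requires and has no effect on sample size or analysis.
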